8.3. Unanticipated Adverse Device Effects (UADE)

An Unanticipated Adverse Device Effect (UADE) is a serious adverse effect on health or safety or any life-threatening problem or death caused by, or associated with, a device, if that effect or problem was not previously identified in nature, severity, or degree of incidence in the investigational plan or application (including a supplementary plan or application), or any other unanticipated serious problem associated with a device that relates to the rights, safety, or welfare of subjects. Anticipated potential adverse device effects have been identified in the sponsor Risk Management files and/or product labeling.

The Principal Investigator will assure that all unanticipated adverse device effect (UADE) involving risk to subjects or others will be reported to the sponsor within 24 hours of knowledge of event. All UADE's will be evaluated and the results of such evaluation will be reported to the IRB within ten (10) working days after the event is reported by the study subjects. The sponsor will report all SAE's and UADE's to the appropriate regulatory authority. All Serious and Unanticipated Adverse Effects will be reviewed by a Medical Monitor.

9. Device Deficiencies

The VSA app is an NSR device, but since the device does not diagnose or provide therapy, no device deficiencies are anticipated.

Software bugs within the VSA app, either found by the study team or reported by the participant will not be considered a device deficiency.

If, at any time during the study, the participant's Smartphone (where the VSA app is installed) physically breaks, or malfunctions, or the VSA app ceases to function or gives unexpected or erroneous information, participants will be instructed to stop using the VSA app and contact the study team. If the participant has another compatible Smartphone, instructions on installing the VSA app on a different Smartphone will be provided and the participants will be instructed on how to remove the VSA app on the first Smartphone (if applicable).

If, at any time during the study, a commercially available (i.e., FDA cleared or approved) device (PAP and associated supplies) physically breaks, or malfunctions, or gives unexpected or erroneous information,

participants will be instructed to contact their DME provider. The DME provider may provide a replacement device or repairs at the sponsor’s discretion. Alternatively, the sponsor may choose to exit the participant without providing a replacement device.

The sponsor will not provide maintenance or support for any commercially available (i.e., FDA cleared or approved) devices (PAP and associated supplies). If a participant reports a device malfunction and/or device complaint to the sponsor support team (Verily User Success), the participant will be instructed to contact their DME provider.

The sponsor support team may contact study participants during study participation in order to troubleshoot issues with the VSA app, such as issues logging in or the app crashing.

10. Investigational Products

10.1. Investigational Product Description

The VSA program/app, is an Obstructive Sleep Apnea (OSA) management platform.

[REDACTED]

10.2. Investigational Product Labeling & Accountability

The Investigator should take adequate precautions, including access to the Investigational product to prevent diversion of the VSA app into unauthorized channels of distribution.

The VSA app is classified as a Mobile Medical App (per FDA Guidance Policy for Device Software Functions and Mobile Medical Applications issued September 2019) under enforcement

discretion. The VSA app will be labeled with the following: "CAUTION--Investigational device. Limited by Federal (or United States) law to investigational use."

Only Institutions/Investigators participating in the clinical study will be eligible to receive the VSA app and can be used only when the following has been received:

- Curriculum Vitae of the Investigator
- A signed Investigator Agreement
- Institutional Review Board (IRB) approval
- IRB-approved Informed Consent Form

11. Regulatory, Ethical and Study Oversight Considerations

11.1. Regulatory and Ethical Considerations

This study will be conducted in accordance with the protocol and with the following:

- Consensus ethical principles derived from international guidelines including the Declaration of Helsinki
- Applicable ICH Good Clinical Practice (GCP) Guidelines
- Applicable laws and regulations

The protocol, protocol amendments, ICF, and other relevant documents (eg, advertisements) must be submitted to an IRB/IEC by the investigator and reviewed and approved by the IRB/IEC before the study is initiated.

Any amendments to the protocol will require IRB/IEC approval before implementation of changes made to the study design, except for changes necessary to eliminate an immediate hazard to study participants.

The investigator will be responsible for the following:

- Providing written summaries of the status of the study to the IRB/IEC annually or more frequently in accordance with the requirements, policies, and procedures established by the IRB/IEC
- Notifying the IRB/IEC of SAEs or other significant safety findings as required by IRB/IEC procedures; and
- Providing oversight of the conduct of the study at the site and adherence to requirements of 21 CFR, ICH guidelines, the IRB and all other applicable local regulations

11.2. Financial Disclosure

Investigators and sub-investigators will provide the sponsor with sufficient, accurate financial information as requested to allow the sponsor to submit complete and accurate financial certification or disclosure statements to the appropriate regulatory authorities, as appropriate. Investigators are responsible for providing information on financial interests during the course of the study and for 1 year after completion of the study.

11.3. Informed Consent Process

Potential participants will be presented with the Baseline Sleep Apnea Study #2 eICF on the Baseline Sleep Apnea Study #2 Web Portal..

Participants must be informed that their participation is voluntary. Participants will be required to sign a statement of informed consent that meets the requirements of 21 CFR 50, local

regulations, ICH guidelines, Health Insurance Portability and Accountability Act (HIPAA) requirements, where applicable, and the IRB.

If the potential participant agrees to the terms described in the Baseline Sleep Apnea Study #2 eICF and provides consent, study eligibility will be further assessed.

11.4. Data Protection

Participants will be assigned a unique identifier by the sponsor. Any participant records or datasets that are transferred to the sponsor will contain the identifier only; participant names or any information which would make the participant identifiable will not be transferred.

The participant must be informed that his/her personal study-related data will be used by the sponsor in accordance with local data protection law. The level of disclosure must also be explained to the participant. All data used in the analysis and reporting of this evaluation will be used in a manner without identifiable reference to the study participant.

11.5. Data Quality Assurance

- All participant data relating to the study will be recorded on printed or electronic CRF unless transmitted to the sponsor or designee electronically (e.g. laboratory data). The Investigator (or designee) is responsible for verifying that data entries are accurate and correct by physically or electronically signing the CRF.
- The investigator must maintain accurate documentation (source data).
- The investigator must permit study-related monitoring, audits, IRB review, and regulatory agency inspections and provide direct access to source data.
- Monitoring details describing strategy (e.g. risk-based initiatives in operations and quality such as Risk Management and Mitigation Strategies and Analytical Risk-Based Monitoring), methods, responsibilities and requirements, including handling of noncompliance issues and monitoring techniques (central, remote, or on-site monitoring) are provided in the Monitoring Plan.
- The sponsor or designee is responsible for the data management of this study including quality checking of the data.
- The sponsor assumes accountability for actions delegated to other individuals (e.g. Contract Research Organizations).
- Records and documents, including signed ICFs, pertaining to the conduct of this study must be retained by the investigator for a minimum of [2] years after study completion unless local regulations or institutional policies require a longer retention period. No records may be destroyed during the retention period without the written approval of the sponsor. No records may be transferred to another location or party without written notification to the sponsor.

11.6. Source Documents

- Source documents provide evidence for the existence of the participant and substantiate the integrity of the data collected.
- If study data is recorded directly on the CRFs/eCRFs (i.e., no prior written or electronic record of data), it is considered to be source data.
- All data will be entered directly into the eCRF, ePRO, and eICF.
- Definition of what constitutes source data can be found in CRF completion guidelines.

11.7. Study and Site Closure

The sponsor designee reserves the right to close the study site (decentralized) or terminate the study at any time for any reason at the sole discretion of the sponsor. Study sites will be closed upon study completion. A study site is considered closed when all required documents and study supplies have been collected and a study-site closure visit has been performed.

The investigator may initiate study-site closure at any time, provided there is reasonable cause and sufficient notice is given in advance of the intended termination.

Reasons for the early closure of a study site by the sponsor or investigator may include but are not limited to:

- Failure of the investigator to comply with the protocol, the requirements of the IRB or local health authorities, the sponsor's procedures, or GCP guidelines
- Inadequate recruitment of participants by the investigator

11.8. Publication Policy

- The results of this study may be published or presented at scientific meetings. If this is foreseen, the investigator agrees to submit all manuscripts or abstracts to the sponsor before submission. This allows the sponsor to protect proprietary information and to provide comments.
- The sponsor will comply with the requirements for publication of study results. In accordance with standard editorial and ethical practice, the sponsor will generally support publication of multisite studies only in their entirety and not as individual site data. In this case, a coordinating investigator will be designated by mutual agreement.

12. Statistical Considerations

The study plans to enroll approximately 50-200 individuals that will be diagnosed with Obstructive Sleep Apnea (OSA) and begin PAP therapy, as part of the study procedures. It is recognized that the sample size achieved in this baseline study will likely be insufficient for statistical hypothesis testing, but it will still be useful for establishing a baseline understanding of the performance of the VSA program. The primary endpoints of interest are five timelines relating to the patient diagnostic and treatment journey:

- Time (number of days) from when participant is told they may have OSA to OSA diagnosis
 - Time (number of days) from when participant is told they may have OSA to when they receive HST prescription
 - Time (number of days) from when participant receives HST prescription to OSA diagnosis
- Time (number of days) from OSA diagnosis to PAP therapy initiation
- Time (number of days) from therapy initiation to when 90-day compliance threshold is achieved

Each of these will be reported as a point estimate accompanied by a confidence interval. These will be calculated from the average and standard deviation of these timeframes across all participants. [REDACTED]

[REDACTED]

[REDACTED]

[REDACTED]

[REDACTED]

- [REDACTED]

[REDACTED]

13. References

1. Types of Sleep-Disordered Breathing. ResMed.
<https://www.resmed.com/ap/en/healthcare-professional/diagnosis-and-treatment/sleep-disordered-breathing/types-of-sleep-disordered-breathing.html>. Accessed September 6, 2019.
2. Spicuzza, Lucia, et al. "Obstructive Sleep Apnoea Syndrome and Its Management." *Therapeutic Advances in Chronic Disease*, vol. 6, no. 5, 2015, pp. 273-285.,
[doi:10.1177/2040622315590318](https://doi.org/10.1177/2040622315590318).

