Participant Duration	For participants who are diagnosed with OSA and prescribed a PAP device, active participation in the study after receiving the PAP device is expected to last approximately 3 months from receipt of the device. Active participation is defined as using the PAP device (PAP data collection) while completing the other study related activities (including VSA app and console use, surveys/questionnaires, and interacting with optional Health Coaches)

	For participants who are diagnosed with OSA and prescribed a PAP device, total participation may last for up to one (1) year, including screening, time to diagnosis, and PAP data collection after active participation in the study has been completed.
Inclusion Criteria	
 1. Ages 18 or older 2. Able to speak and read English 3. Legal United States Resident with a Government Issued ID 4. Participating in the Project Baseline Community Study 5. Demonstrates understanding of the study requirements and is able and willing to sign the informed consent form 6. Own a smartphone with a data plan and be the primary user of the smartphone; smartphone must use Android Lollipop (5.1+ / API 22+) or iOS 11.X+ 7. Own a computer with a web camera 8. Consistent access to electricity and wifi for the duration of the study 9. Have a high risk of OSA as determined by screening questionnaire 10. Good candidate for PAP therapy, in the opinion of the managing clinician 11. Without significant limitation in ability to participate in the study, in the opinion of the investigator.
Exclusion Criteria	
 1. Previously diagnosed with sleep apnea or other sleep disorders, that in the opinion of the investigator, makes the participant ineligible (e.g., Obstructive Sleep Apnea, Central Sleep Apnea, Complex Sleep Apnea, chronic insomnia) 2. Participant is a shift worker (indicated by having a night shift schedule on a regular basis, or a work shift that changes or rotates on a daily, weekly, or monthly basis) 3. Sponsor employees and individuals working on Project Baseline 4. Self reported to be pregnant or planning to become pregnant during the study period 5. Current use of home oxygenation devices, such as supplemental oxygen

[REDACTED]

[REDACTED]	[REDACTED]	[REDACTED]	[REDACTED]
[REDACTED]	[REDACTED]	[REDACTED]	[REDACTED]
[REDACTED]	[REDACTED]	[REDACTED]	[REDACTED]
[REDACTED]	[REDACTED]	[REDACTED]	[REDACTED]
[REDACTED]	[REDACTED]	[REDACTED]	[REDACTED]

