The VSA app is intended to help individuals who may have OSA go through the complex diagnostic pathway more efficiently and virtually. The VSA app is also intended to help patients who have been diagnosed with OSA to manage their therapy and is intended to facilitate a program where users can possibly discover their potential risk for OSA through a clinically validated questionnaire screener and consult with a healthcare professional.

The VSA app will also allow participants to message with Health Coaches who will provide guidance related to sleep and OSA. Communication between the Health Coach and participant is important in enhancing and promoting motivation for PAP adherence. The motivational enhancement approach is a published behavioral intervention based on the principles of motivational interviewing¹². Its fundamental premise is to honor the natural ambivalence that accompanies any change to behavior and to approach the patient in a thoughtful and empathetic manner that elicits critical thought - in order to maximize behavior change.

Technology, especially mobile technology, has the potential to provide new, easier to use, more timely, and more scalable methods for helping patients discover their OSA risk, onboarding patients with OSA to PAP treatment, as well as helping these patients to troubleshoot and make progress in their OSA treatment.

5. **Study Design**

5.1. **Study Objectives and Endpoints**

5.1.1. **Objectives(s)**

Primary:

- To assess and quantify patient journey (e.g., time to diagnosis, time to initiate therapy, patient satisfaction) for users of the VSA program

Secondary:

- To assess patient journey completion rates for users of the VSA program
- To assess and quantify PAP compliance in users of the VSA program

[REDACTED]

5.1.2. **Endpoint(s)**

Primary

- Time (number of days) from when participant is told they may have OSA to OSA diagnosis

- Time (number of days) from when participant is told they may have OSA to when they receive HST prescription
 - Time (number of days) from when participant receives HST prescription to when they receive diagnosis
- Time (number of days) from OSA diagnosis to PAP therapy initiation
- Time (number of days) from therapy initiation to when 90-day compliance threshold is achieved

Secondary

- Completion rates
 - Among individuals who had an HST ordered, % of individuals who completed the HST

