 - Among individuals prescribed a PAP device, % of individuals who filled the order (PAP device delivered to them)
 - Among individuals prescribed a PAP device, % of individuals who used the PAP device at least once during the 90 days
- Compliance Metrics
 - Percent of participants who meet 90 day compliance success criteria, as defined by:
 - ≥ 4 hours per night on 70% of nights during a consecutive 30 day period anytime during the first 90 days

[REDACTED]

[REDACTED]

[REDACTED]

[REDACTED]

[REDACTED]

[REDACTED]

[REDACTED]

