5.2. Overview

This is a single group, unblinded, prospective clinical study to understand the patient diagnostic and treatment journey and PAP therapy compliance for Verily Sleep Apnea (VSA) program users. Participants will enroll remotely and if deemed clinically appropriate will undergo a commercially available and approved home sleep test (HST). Upon confirmation of OSA, the participant will begin using the VSA app to supplement PAP treatment. After 90 days of active participation or in the event of earlier departure from the study, the participant will be given instructions for follow-up care, as indicated. Participants will lose access to the VSA app at the end of the 90 day period.

This study will take a decentralized approach. Recruitment, enrollment, consultation, coaching and active participation with the VSA app will take place remotely.

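### Fifth primary time (PAP initiation to compliance threshold): as visibly worded, the all-participants mean and SD can be formed only for those who reach the threshold

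*Combined protocol and SAP*

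**What the plan says.** Section 5.1.2 and the Protocol Summary list as the last primary endpoint: "Time (number of days) from therapy initiation to when 90-day compliance threshold is achieved". The threshold is at least 4 hours of use on "70% of nights during a consecutive 30 day period anytime during the first 90 days". The same lists include a secondary endpoint: "Percent of participants who meet 90 day compliance success criteria".

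Section 12 gives one rule for all five primary times, a point estimate with a confidence interval: "These will be calculated from the average and standard deviation of these timeframes across all participants". Redacted text follows directly. The visible text gives no censoring rule, no assigned value for people who miss the threshold, and no restriction to achievers. Section 5.6 says that data collection stops at withdrawal and that withdrawn participants may be replaced. Section 12 gives the purpose as a baseline picture of how the program performs, and expects the sample to be too small for hypothesis tests.

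**The concern.** A time that ends when a threshold is reached exists only for people who reach it. The plan measures what percentage do, so it allows that some will not. A mean and SD over everyone therefore cannot be formed from the observed times. What can be formed is a mean over achievers, with an interval based on their number, under a label that claims all participants.

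The label matters because the figure is meant as a baseline for program performance. An achiever mean says how quickly those who succeeded did so. It need not reflect how many succeeded, so a reader who takes it as the typical experience of a starter would be misled.

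**Working it through.** **Inputs from the documents.** The qualifying count is 70% of 30 nights = 21 nights, the horizon is 90 days (Section 5.1.2), and the sample is 50 to 200 (Sections 5.3 and 12). The visible text states no achievement rate, mean, SD or expected time, so there is no plan figure to reproduce. Every other input below is an assumption.

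**Step 1: what the achiever mean leaves out.** Let p be the share of starters who achieve and m the achiever mean. Without withdrawal, the restricted mean to day 90 is R = p·m + (1 − p)·90.

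- With m = 40 and p = 0.9: 36 + 9 = 45 days.
- With m = 40 and p = 0.5: 20 + 45 = 65 days.

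The achiever mean is 40 in both. The gap is (1 − p)(90 − m). For m of 35 to 50 and p of 0.5 to 0.9 it runs from 0.1 × 40 = 4 days to 0.5 × 55 = 27.5 days, and it is zero only if everyone achieves. This is a difference between two summaries, not bias in the achiever mean as a description of achievers.

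**Step 2: direction in a simple case.** Suppose 30% achieve, all at day 30. Then m = 30 and R = 0.3 × 30 + 0.7 × 90 = 72. Now let a further 50% achieve at day 60. Then m = (9 + 30)/0.8 = 48.75 and R = 9 + 30 + 18 = 57. More people achieve and R improves, but m looks worse.

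**Step 3: night-level simulation.** The model has 90 nights per starter and 21 qualifying nights in any 30, dated at the end of the window. In model (a), each person has a constant nightly chance (logit-normal, SD 1.2) and its mean rises from −0.3 to 1.0. In model (b), 40% comply from the start at 0.9 per night. The share who settle in later (from 0.35 to 0.9, after a day between 15 and 45) rises from 0% to 40%, and the rest stay at 0.35.

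| Model | Achieving | Achiever mean | Restricted mean |
|---|---|---|---|
| (a) lower use | 33% | 38.7 | 73.2 |
| (a) higher use | 73% | 34.4 | 49.4 |
| (b) no late settlers | 40% | 30.1 | 66.0 |
| (b) 40% late settlers | 80% | 39.2 | 49.4 |

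In (a) the achiever mean moves the right way, but by 38.7 − 34.4 = 4.3 days against about 24 for the restricted mean. In (b) it rises by 9.1 days while the restricted mean falls by 16.6.

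**Step 4: precision.** The 95% half-widths at n = 50, achiever mean against restricted mean, in the row order above, are 7.4 v 7.1, 3.7 v 7.4, 0.7 v 8.2 and 3.4 v 6.3 days. The restricted mean carries the spread between achievers and non-achievers: its variance is p·SD² + p(1 − p)(90 − m)². With p = 0.4, m = 40 and SD = 15 this is 90 + 600 = 690, most of it from the second term.

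**Step 5: withdrawal.** In model (b) with 20% late settlers (60% achieving, true restricted mean 57.6, n = 200), independent withdrawal of 19% gives 57.6 days by Kaplan-Meier. Counting withdrawals as not achieved gives 61.1. If half the non-achievers withdraw, Kaplan-Meier gives 54.6 days and 66% achieving, and counting withdrawals as not achieved gives 57.6 and 60%. Neither is right in both cases.

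**Step 6: dating.** Achievement could be dated at the qualifying night or at the end of the 30-night window. The same people achieve either way, but a date can differ by up to 30 − 21 = 9 days. In model (b) at 40% achieving, the achiever mean is 23.4 or 30.1 days.

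**The case against.** **Redaction.** The quoted sentence runs straight into redacted text, which is where a rule for non-achievers would naturally sit. A reader might infer that the plan has no such rule, but the documents do not support that. The point is therefore conditional: confirm the rule, or state one. If a rule exists, the visible sentence still has to agree with it.

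**No decision depends on it.** The study is single-group and descriptive. Reading the endpoint among achievers is natural, and the secondary percentage shows the shortfall. With no withdrawal and starters as the denominator, a reader could rebuild R from the two outputs. This limits the harm. It does not correct the label, and the secondary endpoint is stated per participant rather than per starter, so the rebuilt figure need not match.

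**The reversal is constructed.** This stands. In model (a) the achiever mean moves in the right direction. It reverses only in Step 2 and in model (b), where the comparator has no late achievers. A reader might infer that the planned figure will rank program versions backwards, but the visible text plans no such comparison and gives no usage data.

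**A label would be enough.** Marking the mean as among achievers, with its denominator, would cure the mislabelling. It would still leave no primary summary of the fifth time for all starters.

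**The other four times.** A reader might extend the point to all five. Sections 5.3 and 12 describe a population that is diagnosed and begins PAP, for whom the first four times exist. What remains there, including people prescribed PAP who never use it, is a matter of labelling denominators. That, enrolment timing and app access are not part of this point.

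**Conclusion.** The point holds for the fifth primary time on the visible text, and should be fixed. Followed as written, and unless the redacted text says otherwise, Section 12 yields an achiever-only estimate and interval labelled as all participants. Its size cannot be fixed from the documents. Under the assumptions above, the achiever mean lies 4 to 27.5 days below the restricted mean for p of 0.5 to 0.9. It moved about 4 days while achievement rose from 33% to 73%, and it went the wrong way in one constructed night-level case. The consequence is for how a descriptive baseline is read. Error rates are not affected. Confidence is medium because of the redaction.

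**What to change.** If the redacted text already holds a rule for non-achievers, cross-refer to it and make the visible sentence agree. Otherwise amend the sentence for the fifth time:

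- Include everyone who starts PAP, with day 0 at initiation and non-achievers kept to day 90. Count participants who withdraw and are replaced under Section 5.6 in the denominator.
- Report the cumulative proportion achieving by day 90 (Kaplan-Meier, censoring at withdrawal) and the restricted mean to day 90, each with a 95% confidence interval.
- Add a sensitivity analysis counting withdrawals as not achieved, because withdrawal may be linked to poor PAP use.
- Keep the achiever mean and SD as a supplementary line labelled as among achievers, with number achieving over number starting.
- State whether achievement is dated at the qualifying night or at the end of the 30-night window.

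The cost is wording and a little more analysis, from initiation dates and nightly use that the endpoints already need. The headline becomes longer: about 49 to 73 days instead of 30 to 39 in the simulated cases. It depends on the day-90 cut, which must be stated with it. Its interval is often about twice as wide as the achiever-only interval or wider (three of the four simulated cases), because it describes all starters.
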